## 2.0 Project Management

### 2.1 Research Staff and Qualifications

Study personnel are experts in designing and running clinical trials and do so as part of their positions at Rutgers

### 2.2 Research Staff Training

[REDACTED]

All persons assisting with the research will be informed about the protocol, the procedures, and their duties and functions during research meetings.

### 2.3 Resources Available

Facilities at CINJ and RWJUH will be used for the purposes of this study.

### 2.4 Research Sites

Rutgers Cancer Institute of New Jersey and Robert Wood Johnson University Hospital.

## 3.0 Multi-Center Research

N/A

## 4.0 Subject Considerations

### 4.1 Subject Selection and Enrollment Considerations

#### A. Method to Identify Potential Subjects

Patients will be recruited from the clinical practice of the Hematologic Malignancies Tumor Study Group of Rutgers Cancer Institute of New Jersey.

#### B.

[REDACTED]

#### C. Subject Screening

##### Inclusion Criteria

**A patient/subject is eligible for enrollment if all of the following inclusion criteria are met.**

Histologically proven AML or advanced myeloid malignancy [myelodysplasia; chronic myelomonocytic leukemia (CMML); or chronic myeloproliferative disease (MPD) each with  $\geq 10\%$  myeloblasts in blood or bone marrow];

For patients with *de novo* AML: must not be a candidate for standard induction therapy based upon age, co-morbidities, patient choice, high risk features known to have poor outcomes with standard induction therapy (ELN high risk disease by cytogenetics, DNA mutation profile or TP53 mutation);

Patients with advanced MDS, secondary AML, relapsed/refractory AML, who have received prior treatment with hypomethylating agents are eligible;

Patients must give informed consent.

Patients must have an ECOG performance status  $\leq 2$  (Appendix A).

Patients must have normal organ function as defined below:

- Total bilirubin  $< 2 \times$  ULN
- AST(SGOT)/ALT(SGPT)  $\leq 2.5 \times$  institutional ULN
- Creatinine clearance  $> 30$  ml/min

#### **Exclusion Criteria**

**A patient /subject will not be eligible for this study if any of the following exclusion criteria are met.**

*WBC uncontrolled ( $>15,000/uL$ ) despite hydroxyurea x 5 days (see below).*

Known CNS AML.

Serious concomitant systemic disorders (including active infections) that would compromise the safety of the patient or compromise the patient's ability to complete the study, at the discretion of the investigator. Pregnant patients are excluded.

Age  $< 18$  years. Because no dosing or adverse event data are currently available on the use of Salsalate in combination with venetoclax and decitabine in patients  $< 18$  years of age, children are excluded from this study. Salicylates have also been associated with Reyes syndrome in pediatric patients.

History of allergic reactions attributed to compounds of similar chemical or biologic composition to Salsalate or other agents used in the study. Examples include aspirin.

The effects of venetoclax and decitabine or 5-azacytidine on the developing human fetus at the recommended therapeutic dose are unknown. For this reason and because therapeutic agents used in this trial are known to be teratogenic, women of child-bearing potential and men must agree to use adequate contraception (hormonal or barrier method of birth control; abstinence) prior to study entry, for the duration of study participation and for 24 weeks after. Should a woman become pregnant or suspect she is pregnant while participating in this study, she should inform her treating physician immediately.

Patients with immune deficiency are at increased risk of lethal infections when treated with marrow-suppressive therapy, therefore, known HIV-positive patients receiving combination anti-retroviral therapy are excluded from the study because of possible pharmacokinetic interactions with treatment medications or other agents administered during the study.

### **4.3 Number of Subjects**

#### **A. Total Number of Subjects**

Twenty at Rutgers CINJ. Total = 20 patients.

#### **C. Feasibility**

Based on the number of patients seen at CINJ/RWJUH with AML, MPN, or MDS meeting recruitment goals within the timeframe is expected.

#### **4.4 Consent Procedures**

##### **A. Consent Process**

Informed consent will be obtained prior to commencing any research procedures. The investigators will seek consent only under circumstances that provide the prospective patient opportunity to consider whether or not to participate and that minimizes the possibility of coercion or undue influence. The information given to the patient, or the representative, shall be in a language understandable to the subject or representative. The informed consent document may not include any exculpatory language through which the subject or representative is made to waive any of the subject's legal rights or releases, or appears to release the investigator, the sponsor or the institution from liability for negligence

##### **C. Documentation of Consent**

###### **▪ Documenting Consent**

Individuals will be asked to sign an informed consent document

**Waiver of Documentation Of Consent (i.e., will not obtain subject's signature)**

N/A

#### **4.5 Special Consent/Populations**

##### **A. Minors-Subjects Who Are Not Yet Adults**

No dosing or adverse event data are currently available on the use of Salsalate in combination with venetoclax and decitabine in patients <18 years of age. Pediatric patients who receive salicylates are also at risk for Reyes syndrome. Therefore, minors will not participate in this study

##### **B. Wards of the State**

N/A

##### **C. Non-English-Speaking Subjects**

###### **▪ Process for Non-English-Speaking Subjects**

Non English speakers will not be enrolled because this is an investigator-initiated study without funding source.

[figure not shown]
###### **▪ Short Form Consent for Non-English Speakers**

This will not be used.

##### **D. Adults Unable to Consent / Cognitively Impaired Adults (for interventional studies)**

Those unable to consent or cognitively impaired will not be asked to enroll in this trial.

#### **4.6 Economic Burden and/or Compensation for Subjects**

The study is an investigator-initiated clinical trial with no financial support. Philanthropic funds will be used to pay for study drug (SALSALATE). The additional medications are standard of care and will be financed based upon the patients insurance.

#### **4.7 Risks of Harm/Potential for Benefits to Subjects**

##### **A. Description of Risks of Harm to Subjects**

MDS, AML and related advanced myeloid disorders are life-threatening diseases. Risks of the disease include bleeding, infection and organ dysfunction. The disease is fatal with standard chemotherapy in > 80% patients eligible for this study over a 2 years. The combination of venetoclax + hypomethylating agent therapy is a breakthrough – greatly improving response rates and, likely, also survival. The potential risks of this study are that there will be toxicity from the study drug related to known SALSALATE toxicities (e.g tinnitus, renal insufficiency) or that it will interfere with the anti-leukemic effect of venetoclax + hypomethylating agent. To protect against or minimize potential risks, we will monitor toxicity real time and have imposed very strict stopping rules.

##### **B. Potential Benefits to Subjects**

SALSALATE has been safely administered to patients undergoing intense AML induction therapy. It is also routinely used as a supportive care medication during AML therapy. We believe it has the potential to enhance the anti-leukemic effects of standard venetoclax + hypomethylating agent therapy and improve response rates and duration of remission.

#### **5.0 Special Considerations**

N/A

#### **6.0 Data Management Plan**

##### **6.1 Data Analysis**

1. An unacceptable adverse event is defined as a Grade 3 study drug (SALSALATE) related or possibly related irreversible (i.e. doesn't reverse within one week) event with the exception of:
  - a. Grade 3 fever, asthenia or constipation.
  - b. Grade 3 nausea, vomiting, diarrhea (not requiring tube feeding, total parenteral nutrition, or prolonged hospitalization;
  - c. Grade 3 infection, bleeding or expected complications of cytopenias due to leukemia or decitabine + venetoclax treatment;
  - d. Grade 3 or 4 tumor lysis syndrome successfully managed clinically that resolves within 7 days without end organ damage; or
  - e. Grade 3 or 4 isolated electrolyte abnormalities that last < 72 hours.

We consider an adverse event rate of 7% or higher to be unacceptably high, so we will stop the trial if, at any point, we are 80% certain that the rate is 7% or higher. In the following table, the shaded cells in the table indicate the region where we are 80% certain that the rate exceeds 7%.

According to this table, if there is 1 unacceptable (grade 3) SALSALATE related or possibly related adverse event (defined above) among the first 10 patients, or if there are 2 unacceptable adverse events among the first 20 patients, the trial will be stopped for unacceptable toxicity.

This table was calculated using a Bayesian posterior beta distribution, assuming a uniform prior.

N patients      k: number of unacceptable toxicities

	0	1	2	3
3	0.748052	0.973272	0.9987	0.999976
4	0.695688	0.957507	0.99692	0.999887
5	0.64699	0.939179	0.994161	0.999679
6	0.601701	0.918726	0.990312	0.999293
7	0.559582	0.896534	0.985301	0.998664
8	0.520411	0.872948	0.979088	0.997729
9	0.483982	0.84827	0.971658	0.996424
10	0.450104	0.82277	0.963021	0.99469
11	0.418596	0.796683	0.953203	0.992473
12	0.389295	0.770217	0.942247	0.989724
13	0.362044	0.743553	0.930205	0.986401
14	0.336701	0.716847	0.917139	0.982467
15	0.313132	0.690237	0.903119	0.977894
16	0.291213	0.663839	0.888217	0.97266
17	0.270828	0.637756	0.87251	0.966749
18	0.25187	0.612071	0.856078	0.960152
19	0.234239	0.586857	0.838997	0.952867
20	0.217842	0.562173	0.821347	0.944896

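### Section 6.1 is inconsistent on whether Grade 4 events count toward the trial-level toxicity stopping rule, and silent on Grade 5

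*Combined protocol and SAP*

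**What the plan says.** All the text that decides the count is in section 6.1, Data Analysis.

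- **Definition:** "An unacceptable adverse event is defined as a Grade 3 study drug (SALSALATE) related or possibly related irreversible", followed by a one-week test of reversibility and a list of exceptions ("reverse within one week) event with the exception of").
- **Stopping sentence:** the trial stops at "1 unacceptable (grade 3) SALSALATE related or possibly related adverse event (defined above) among the first 10 patients", or at two such events among the first 20.
- **Exceptions naming Grade 3 only:** (a) reads "Grade 3 fever, asthenia or constipation". Exception (b), on gastrointestinal symptoms managed without feeding support or a longer hospital stay, carries the same grade limit. So does (c), whose words are "Grade 3 infection, bleeding or expected complications of cytopenias due to leukemia or decitabine + venetoclax treatment".
- **Exceptions naming Grade 3 or 4:** (d) reads "Grade 3 or 4 tumor lysis syndrome successfully managed clinically that resolves within 7 days without end organ damage". Exception (e) opens "Grade 3 or 4 isolated electrolyte abnormalities that last" and sets a limit of under three days.

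Grade 5 does not appear in 6.1, and neither the definition nor the stopping sentence extends to higher grades. The boundary comes from a posterior beta distribution with a uniform prior. The trial stops once there is 80% certainty that the event rate is at least 7%.

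**The concern.** There are two separate defects. For Grade 4 the text is inconsistent: the definition and the stopping sentence confine the event to Grade 3, while two exceptions are written as if Grade 4 events needed exempting. For Grade 5 the text is silent.

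A third question follows if higher grades do count. Exceptions (a) to (c) exempt only the Grade 3 forms of their events, so it is unclear whether a Grade 4 or 5 infection or bleed is exempt as well.

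Tolerability is the primary objective (section 1.1 A). In the visible documents 6.1 holds the only trial-level toxicity rule with a stated boundary, and section 4.7 A relies on strict stopping rules to protect patients. Two careful readers could count different k from the same patients and reach opposite decisions, and they would differ over the most severe events.

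**Working it through.** **1. Does another section settle the grade?**

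| Place | What it governs | Does it say what adds to k? |
|---|---|---|
| 1.3 A, salsalate hold for Grade 3 or 4 related non-hematologic events | The individual patient's dosing | No |
| 1.3 A, reasons for ending treatment | The individual patient; unacceptable events and life-threatening toxicity are separate items | No |
| 1.3 A, notice of deaths and other serious events | Reporting to the IRB | No |
| 6.3 A, weekly review | Review of data | No |
| 6.2, monitoring plan cited | Not reproduced | Cannot be seen |
| 6.3 B, monitoring board | Heading with no visible text | Cannot be seen |

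Exceptions (d) and (e) suggest that Grade 4 was in mind but do not prove it. Tumor lysis that resolves within 7 days, and electrolyte changes lasting under 72 hours, already fail the one-week irreversibility test at any grade.

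**2. Reproduce the plan's table.** With a uniform prior, the posterior after k events in n patients is Beta(1+k, 1+n−k). Its tail above 0.07 equals the probability that a Binomial(n+1, 0.07) count is at most k.

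- n=10, k=0: 0.93^11 = 0.4501.
- n=10, k=1: 0.4501 + 11 × 0.07 × 0.93^10 = 0.4501 + 0.77 × 0.48398 = 0.8228.
- n=20, k=1: 0.93^21 + 21 × 0.07 × 0.93^20 = 0.21784 + 1.47 × 0.23424 = 0.5622.
- n=20, k=2: 0.5622 + 210 × 0.0049 × 0.93^19 = 0.5622 + 1.029 × 0.25187 = 0.8213.

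These match the printed values. All 72 cells (n=3 to 20, k=0 to 3) reproduce to within 4.7e-07, so the table is sound. The defect lies in what feeds k.

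**3. Effect of counting or not counting one Grade 4-5 event**, against the 0.80 threshold:

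| n | Events already counted | Not counted | Counted |
|---|---|---|---|
| 3 | 0 | 0.748 (continue) | 0.973 (stop) |
| 10 | 0 | 0.450 (continue) | 0.823 (stop) |
| 12 | 1 | 0.770 (continue) | 0.942 (stop) |
| 20 | 1 | 0.562 (continue) | 0.821 (stop) |

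The first two rows bracket n=3 to 10, where the decision flips at every n. The last two bracket n=12 to 20, where it flips only if one event has already been counted.

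**4. Illustration of the chance of stopping.** Let p be the rate of counted events, q = 1−p, with at most one event per patient and each outcome known in turn. The trial continues through patient 20 only with no event in the first 10 and at most one in the next 10:

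P(stop by 20) = 1 − q^10 × (q^10 + 10 p q^9).

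Suppose the true rate of qualifying events of all grades is 7%, and a share s of them is Grade 4-5 and not counted, so p = 0.07 × (1−s).

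- s=0: p=0.07; 1 − 0.48398 × (0.48398 + 0.36429) = 0.590.
- s=5%: p=0.0665; result 0.568.
- s=10%: p=0.063; result 0.545.
- s=30%: p=0.049; result 0.445.
- s=50%: p=0.035; 1 − 0.70028 × (0.70028 + 0.25399) = 0.332.

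The share s is an assumption throughout, because the documents give none.

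**The case against.** The strongest reply is that the intent is clear enough. Exceptions (d) and (e) would be odd if Grade 4 lay outside the definition. The patient-level hold in 1.3 A pairs the same one-week test with Grade 3 or 4 events. A rule under which a drug-related death does not count is the least plausible reading. This stands as a statement of likely intent. It does not settle the text, because the protocol writes Grade 3 or 4 elsewhere when it means both, and (d) and (e) are redundant under the one-week test in any case. Nor does it answer which grades (a) to (c) exempt.

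A second reply is that severe events would be noticed anyway. That is correct: they are graded, reported and reviewed weekly (1.3 A and 6.3 A). A reader might infer that Grade 4-5 events would go unseen, or that the plan means to ignore deaths. The documents support neither. The gap is confined to whether such events move the stopping count.

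A third reply is that the effect may be small. Salsalate is given only from day 5 to the end of the hypomethylating agent, and section 1.1 B reports no adverse effects of an earlier salicylate given with induction chemotherapy. A low Grade 4-5 share is therefore compatible with the documents, and at 5% the stopping chance moves only from 59% to 57%. This stands for the average effect. It does not alter step 3, where a single event decides.

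**Conclusion.** The concern holds: 6.1 is inconsistent on Grade 4 and silent on Grade 5, and followed literally its stopping rule omits the most severe salsalate-related events. The single-event effect rests on the plan's table alone for n=3 to 10. For n=12 to 20 it also needs one event already counted. The fall in stopping probability from 59% to between 57% and 33% rests on an assumed share of 5% to 50% and a true rate of 7%, and is an illustration only.

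Two stronger readings should be resisted.

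- A reader might infer that one event decides the outcome at every tabulated n. It does not. With no event counted by n=11 to 20, a first event leaves the posterior between 0.797 and 0.562, so the trial continues either way. Two counted events at n=11 cannot arise when outcomes are known in sequence with at most one per patient, because reaching patient 11 requires none in the first 10.
- A reader might use the adverse event rates in section 1.2 to predict extra stops. Those figures are labelled grade 3, with no attribution or duration, and so say nothing about unresolved Grade 4-5 events possibly related to salsalate.

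The conclusion is limited to the visible documents, since the cited monitoring plan and any monitoring board text cannot be read.

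**What to change.** In 6.1, reconcile the definition, the grade in the stopping sentence and all five exceptions, so that they state consistently:

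1. whether Grade 4 events related or possibly related to salsalate add to k;
2. whether Grade 5 events so attributed add to k;
3. which grades each of (a) to (e) exempts, including Grade 4-5 forms of the events in (a) to (c).

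The threshold is the sponsor's decision, and none is proposed here.

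The cost is a wording change within one section. The posterior table and the boundaries of one event in 10 and two in 20 depend only on n and k, so nothing needs recalculating. The downside is that the trial may stop more often if higher grades count. The sponsor should therefore confirm that the 7% limit suits the reconciled definition.

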#### A. Objectives

Primary Objective: Determine the tolerability of the addition of standard dose Salsalate to the standard treatment combination of venetoclax + HMA (decitabine or 5-azacytidine).

Secondary Objective: Determine the remission rate and, when feasible, perform exploratory studies of: (i) patterns of mutation clearance; and (ii) distribution of cells with low and high reactive oxygen species (ROS) content at various points during therapy.

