Venetoclax dosing will be modified in the context of concurrent use of CYP3A4 or Pgp inhibitors. Venetoclax will be dosed at 70mg /d (if concurrent posaconazole) or 100 mg/d if there is concurrent use of other strong CYP3A4 inhibitors or 200 mg/d if use of moderate CYP3A4 inhibitors. Venetoclax will be dosed at 200 mg/d in the setting of concurrent use of moderate CYP3A4 inhibitors. Dosage should be modified and timing of dose adjusted if concurrent PgtP inhibitors are used. All concurrent meds will be reviewed and dosing schedules approved by a research pharmacist.

**TABLE 1** Commonly used CYP3A4 inhibitors

Moderate	Strong
Aprepitant	Clarithromycin
Cimetidine	Itraconazole
Cyclosporine	Ketoconazole
Erythromycin	Voriconazole
Fluconazole	Posaconazole
Verapamil	Ritonavir
Isavuconazole	Darunavir
Diltiazem	Atazanavir

If the patient has profound thrombocytopenia (< 10,000/uL at day 21 – 28 in the first cycle) a BM asp and biopsy may be performed at the discretion of the treating physician with the option to hold venetoclax. The start of the second cycle is at the discretion of the treating physician and may include modifications of decitabine/5-azacytidine or venetoclax dosing as per standard recommendations. These additional cycles (starting at cycle 2 are not considered part of this clinical trial).

Any Grade 3 or 4 non-hematologic adverse event thought to be Salsalate-related will require the dose to be held until the event recovers to Grade 2 or less. If the adverse event does not resolve within 1 week, the patient will be removed from the study. For Salsalate these events include renal insufficiency, gastritis, tinnitus, vertigo and unanticipated GI bleeding as common toxicities; the Salsalate-relatedness of other toxicities will be assessed by the research team in real time.

Patients will receive full supportive care therapies per Leukemia Tumor Study Group practices concomitantly during the study. No other chemotherapy, immunotherapy, hormonal cancer therapy, radiation therapy, surgery for cancer, or experimental medications will be permitted while the patients are participating in the treatment component of this study (first 2 cycles).

CSFs are not permitted as primary prophylactics. If, in the investigator's opinion, it is required in the presence of severe neutropenia (ANC <500/ $\mu$ l for at least 3 days or concurrent neutropenia and infection) then use of CSFs is allowed per treatment plan described above.

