All "unexpected" (defined below) and/or "serious" experimental drug related adverse events occurring during the active portion of therapy, or up to 30 days after the last dose of treatment, will be reported to the Office of Human Research Services at [contact] or [contact]. Events will be promptly reported, in writing, to the local IRB in accordance with IRB policy. If a death occurs the IRB will be notified within 24-hours of initial receipt of information. All other SAEs must be reported to the IRB within three to ten days of initial receipt of information. Written follow-up reports are required when additional information is needed to fully characterize the event. Copies of each report sent to the IRB will be kept in the study regulatory file.

In addition to reporting to the local IRB, reporting to external bodies such as industry and/or the FDA may be necessary

In the absence of treatment delays due to adverse events, treatment may continue until one of the following criteria applies:

- a) Disease progression/relapse during active treatment,
- b) Intercurrent illness that prevents further administration of treatment,
- c) Unacceptable adverse event(s).
- d) In the event of any drug-related life-threatening toxicity or laboratory abnormality the patient will be withdrawn from further treatment,
- e) Patient decides to withdraw from the study,
- f) Noncompliance with treatment plan,
- g) General or specific changes in the patient's condition render the patient unacceptable for further treatment in the judgment of the investigator, or
- h) Protocol violation - any patient found to have entered this study in violation of the protocol might be discontinued from the study at the discretion of the Principal Investigator.
- i) The desired level of compliance is  $\geq 75\%$ . Patients who cannot maintain this level of compliance may be removed from the study.

Evaluations	Pre-Study (within 2 weeks)	Daily during treatment with decitabine or 5-azacytidine	Prior to Next Treatment
Initial History & Physical	X		
Interim History & Physical		X while hospitalized	X
Toxicity Assessment		X	X
Concomitant Medications	X	X	X
ECOG Performance Status	X		X

CBC, differential, platelets	X 	X while hospitalized	X
Serum Chemistries 	X	X while hospitalized	X
Tumor lysis monitoring and treatment)		X (q8h during ramp up and qd while hospitalized)	
Liver Enzymes 	X	X while hospitalized	X
EKG	X		

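### The trial-stopping rule in 6.1 counts only Grade 3 events that persist beyond one week: read literally it omits Grade 4 and fatal Salsalate events, and on any reading it omits a life-threatening event that reverses within a week

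*Combined protocol and SAP*

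**What the plan says.** The primary objective in 1.1 A is to "Determine the tolerability of the addition of standard dose Salsalate" to venetoclax plus a hypomethylating agent (HMA). The only numerical decision rule for it is in 6.1 Data Analysis. The definition of what counts as unacceptable reads: "defined as a Grade 3 study drug (SALSALATE) related or possibly related irreversible (i.e. doesn't reverse within one week) event". Exceptions (a) to (e) then apply. The trial stops "if there is 1 unacceptable (grade 3) SALSALATE related or possibly related adverse event (defined above) among the first 10 patients"; a second trigger is 2 such events in the first 20. The limits are a 7% event rate and 80% posterior certainty under a uniform prior.

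Four other statements bear on the definition:

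- Exception (d) in 6.1: "Grade 3 or 4 tumor lysis syndrome successfully managed clinically that resolves within 7 days without end organ damage".
- Exception (e) in 6.1: "Grade 3 or 4 isolated electrolyte abnormalities that last < 72 hours".
- Discontinuation criterion (d) in 1.3 A: "In the event of any drug-related life-threatening toxicity or laboratory abnormality the patient will be withdrawn from further treatment". It sets no condition on reversibility.
- The dose-hold rule in 1.3 A: "Any Grade 3 or 4 non-hematologic adverse event thought to be Salsalate-related will require the dose to be held". The hold lasts until recovery to Grade 2 or less, and the patient leaves the study if the event has not resolved within 1 week.

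Section 4.7 A relies on the rule as a protection for patients: "we will monitor toxicity real time and have imposed very strict stopping rules".

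**The concern.** A toxicity stopping rule should respond at least as readily to the worst events as to milder ones. Here the definition combines a grade label that names Grade 3 only with a persistence condition that applies to every event. The label is repeated in the stopping sentence, so it is hard to dismiss as a single slip. Anyone applying the text as written would record zero for a Salsalate-related death. They would also record zero for a life-threatening renal or gastrointestinal bleeding event that improved within days of holding the drug. Section 1.3 A lists renal insufficiency and unanticipated GI bleeding among the Salsalate toxicities.

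Because a single event in the first 10 patients stops the trial, how one such event is classified decides whether the trial continues.

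**Working it through.** **Inputs.** From 6.1: the definition, exceptions (d) and (e), the 7% and 80% limits, the uniform prior, the stopping counts and the printed table. From 1.5: 20 patients. Assumptions: a life-threatening event is graded 4, and reversal, which 6.1 does not define, means recovery to Grade 2 or less, as in the dose-hold rule.

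**Step 1: reproduce the plan's table.** With k events in n patients and a uniform prior, the posterior is Beta(1 + k, 1 + n − k). P(rate > 0.07) then equals the probability that a Binomial(n + 1, 0.07) count is at most k.

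- 0/10: 0.93^11 = 0.450
- 1/10: 0.93^11 + 11 × 0.07 × 0.93^10 = 0.450 + 0.373 = 0.823
- 0/20: 0.93^21 = 0.218
- 2/20: 0.218 + 21 × 0.07 × 0.93^20 + 210 × 0.07² × 0.93^19 = 0.218 + 0.344 + 0.259 = 0.821

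All 72 printed cells are reproduced, and the stated counts follow from them: with one event the 80% limit is passed up to n = 10 (0.823) and not at n = 11 (0.797). The table is correct. The question is what enters k.

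**Step 2: contribution to k of one Salsalate-related or possibly related event that no exception covers.**

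| Event | Literal Grade 3 | Read as Grade 3 or higher | Definition proposed below |
|---|---|---|---|
| Grade 3, not reversed in a week | 1 | 1 | 1 |
| Grade 3, reversed in a week | 0 | 0 | 0 |
| Grade 4 non-hematologic, not reversed in a week | 0 | 1 | 1 |
| Grade 4 non-hematologic, reversed in a week | 0 | 0 | 1 |
| Grade 5 | 0 | 1 | 1 |

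**Step 3: do exceptions (d) and (e) do anything?** An event under (d) is over within 7 days, and one under (e) in under 72 hours (3 days). Both reverse within one week, so both already fail the definition and there is nothing left to exempt. This holds whether reversal means recovery to Grade 2 or full resolution.

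**Step 4: effect of one event.** One Grade 4 event in the first 10 patients that reverses within a week is 0/10 as written (0.450, continue) and 1/10 if counted (0.823, stop). Two in 20 are 0/20 (0.218) or 2/20 (0.821).

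**Step 5: illustration only.** The documents give no rate for the omitted events. At an assumed per-patient rate p of counted events, the trial continues only with none in the first 10 and at most one in the next 10:

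P(stop) = 1 − [(1 − p)^20 + 10p(1 − p)^19]

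| Assumed rate of omitted events | P(stop) as written | P(stop) if counted |
|---|---|---|
| 2% | 0 | 0.20 |
| 5% | 0 | 0.45 |
| 10% | 0 | 0.74 |

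These rows assume no other countable events. If a further 2% of patients, taken as different patients, have events that already count, P(stop) is 0.20 as written and 0.37, 0.59 or 0.82 if the omitted events count.

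**The case against.** The strongest reply is that the one-week clause is deliberate. The dose-hold rule in 1.3 A applies a one-week test to Salsalate-related non-hematologic events of Grade 3 or 4 alike, so 6.1 matches how individual patients are managed. This stands, and it means that leaving out reversible Grade 4 events may be a choice. It does not explain a label that, taken literally, leaves out persistent Grade 4 events and deaths.

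A reader might infer that 6.1 contradicts itself, so that a reversible life-threatening event scores 0 or 1 depending on which part is followed. The text does not support that. Exceptions only subtract, and no part of 6.1 gives such an event a count of 1. Exceptions (d) and (e) could be cautious repetition, so what they show about intent is inference.

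A reader might also see a conflict with discontinuation criterion (d). That criterion governs the individual patient, covers toxicity of any drug in the regimen, and is listed separately from unacceptable adverse events. A patient-level and a trial-level rule may differ. The comparison shows only that the plan regards such events as serious enough to end treatment.

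Nor are patients left unprotected. Dose holds, withdrawal, IRB reporting, weekly review by the investigator (6.3 A) and audits under the institution's monitoring plan (6.2) all remain, and the trial could be stopped by judgement. Salsalate exposure is short: days 5 to 10 with decitabine (6 days) or 5 to 7 with 5-azacytidine (3 days). Section 1.1 B reports no adverse effects of a related salicylate given with induction chemotherapy. The higher rates in Step 5 therefore have no support in the documents.

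Finally, widening the event while keeping 7% makes a stricter rule, and background toxicity is common: section 1.2 cites fever with neutropenia in 43% on venetoclax plus HMA. Without care over exception (c), possibly related events could cause false stops. This is a fair constraint on the fix.

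**Conclusion.** The point holds as a defect in the definition of the counted event. As written, the rule does not count Grade 4 or fatal Salsalate-related events. Under the more generous reading it still does not count a life-threatening event that reverses within a week. Exceptions (d) and (e) have no effect, which suggests but does not establish that a wider definition was meant.

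The size is one event: in the first 10 patients it separates 0.450 (continue) from 0.823 (stop). That contrast needs no assumed rate; the stopping probabilities in Step 5 do and are illustrations. The conclusion about reversible events depends on reading reversal as recovery to Grade 2 or less. If it means full resolution, only events fully resolved within a week are omitted. The conclusion about the literal Grade 3 label does not depend on this.

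**What to change.** Reword the definition in 6.1 along these lines: *An unacceptable adverse event is a Salsalate related or possibly related event that is (i) Grade 3 and has not recovered to Grade 2 or less within one week of onset, or (ii) non-hematologic Grade 4, or Grade 5, whatever its duration, with exceptions (a) to (e).* Exceptions (d) and (e) then have work to do for Grade 4 events.

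- Extend exception (c) to Grade 4 and 5 infection, bleeding or cytopenia complications due to leukemia or to venetoclax plus HMA, but not to events judged Salsalate-related, such as GI bleeding.
- Do not import the laboratory-abnormality wording of discontinuation criterion (d), which could bring hematologic Grade 4 values into the count.
- In the stopping sentence, replace the bracketed grade with *as defined above*.
- Keep the 7% and 80% limits and the table. The investigators should confirm that 7% suits the wider event.

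If the investigators do intend the one-week test to apply to Grade 4, as in the dose-hold rule, the minimum change is *Grade 3 or higher, including any Grade 5* in both places, with the inoperative exceptions (d) and (e) deleted.

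The cost is protocol wording. Grade, start and stop dates and attribution are already collected under 1.3 A, and no visits or patients are added. The downside is that the trial may stop somewhat more often: at an assumed 2% rate of newly counted events and no others, the chance of stopping is 0.20 instead of 0.
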